9.1 Adverse Experiences

The investigators will monitor the subjects closely for any local or systemic adverse events from the study. If any such events are noted, they will be managed appropriately and reported. Subjects will be followed until satisfactory resolution. The description of the adverse event will include time of onset, duration, severity, etiology, relationship to the study (none, unlikely, probably, highly probable) and treatment that was required.

9.2 Premature Discontinuation

Subjects may be discontinued from the study if the investigators decide that it is in the best interest of the subject, or the subject requests to be withdrawn. Subjects' participation will be terminated if any significant depression is identified on the collected information on depression. Subjects will also be referred to a mental health professional.

9.3 Potential Risks

Use of motion sensors. There are no known risks associated with the use of the instrumented motion sensors. The trunk and leg motions made in the proposed research are well within the normal range of motion of adult subjects, and there are no physical injuries expected from the use of the motion sensors. Fatigue from the repeated movement of legs, or dizziness from the computer screen are a possibility.

Surface electrodes. Surface electrodes for recording of muscle activity via electromyography (EMG) and transcutaneous spinal cord stimulation are widely used and present a low-risk to the subject. Skin redness, dryness, or irritation is possible from the shaving and skin cleaning required for the application of the surface EMGs. Skin lacerations from shaving due to dry contact or repeated shaves are possible. Subjects are instructed that they may stop any procedure at any time with no adverse consequences.

Transcutaneous spinal cord and peripheral nerve stimulation. Unpleasant or even painful paresthesia could be experienced during stimulation. In most cases, stimulation parameters can be adapted to be tolerated by the subject. However, there is a likelihood that stimulation cannot be tolerated by a subject. Subjects are instructed that they may stop any procedure at any time with no adverse consequences.

Autonomic dysreflexia (AD) is an acute episodic hypertension resulting from sympathetic hyperactivity⁴⁶ and is typically defined as increased systolic blood pressure greater than 20 to 30 mmHg⁴⁷. AD may be experienced by individuals with injuries above the 6th thoracic level (T6), most commonly triggered by noxious irritation of urinary bladder or colon⁴⁸, although it can also be triggered by nonnoxious or noxious stimuli^{47,49}. A recent study testing the use of tSCS for upright posture in children with SCI detected an episode of AD in one participant (5% occurrence), rating it as "very unlikely to occur"⁵⁰. The stimulation was immediately stopped, and, within 3 min, the episode resolved, and blood pressure returned to baseline levels. Although a study specifically investigating the incidence of AD by spinal cord stimulation in people with SCI failed to observe an adverse event⁵¹, and numerous other studies have not reported incidences of AD^{10,11,32,52-55},

we found two other studies reporting signs of AD in SCI while using SCS^{56,57}. In one study, one out of nine participants was observed to experience symptoms of AD, but was later found to have an injury to the left calf, likely due to the sit-to-stand training paradigm⁵⁷. Although the other study mentions that there were no confirmed incidents of AD, one out of fifteen participants demonstrated an elevation of systolic blood pressure greater than 60 mmHg, and the stimulation was stopped.

History of AD is already an exclusion criteria of our study, and participants with SCI typically have experience in identifying the onset of AD symptoms. However, we believe that although the risk of inducing AD through tSCS may be rare, it is important to monitor blood pressure and other signs of AD (decreased heart rate, face flushing, headache, and sweating) to manage it in time should it occur.

Transcranial magnetic stimulation. The TMS device to be used is the MagStim 200² with a 110mm double cone coil and an EMG interface module. The TMS devices are non-significant risk devices. The principal component of the TMS is a “figure-8” coil made of insulated copper bus bar and capacitor-containing booster modules. The flow of electricity through the coil is regulated by a control module and a computer. When electricity flows through the coil, a magnetic field pulse is generated according to Faraday’s law. This magnetic pulse in turn causes nearby neurons to discharge in a physiological variant of the Hall effect. No electrical current is ever passed between the machine and the participant. Currently, this MagStim 200² machine has FDA approval for peripheral nerve stimulation, but we will use it for cortical stimulation to evoke motor evoked potentials from the motor cortex^{15,24,71,72}.

Generally, TMS is considered safe and well-tolerated. Patients receiving repetitive TMS, which has increased risks compared to single-pulse TMS⁷⁴ (Table 1), are able to drive home or return to work immediately after a repetitive TMS session. In this study, we will only use single-pulse TMS. The single-pulse TMS techniques performed in this study have been used extensively in thousands of research studies and on tens of thousands of participants in the United States and around the world. Single-pulse TMS techniques are considered remarkably safe⁷⁴ if the appropriate guidelines are followed⁷⁵.

Table 1

Potential side effects of TMS. Consensus has been reached for this table.

Side effect	Single-pulse TMS	Paired-pulse TMS	Low frequency rTMS	High frequency rTMS	Theta burst
Seizure induction	Rare	Not reported	Rare (usually protective effect)	Possible (1.4% crude risk estimate in epileptic patients; less than 1% in normals)	Possible (one seizure in a normal subject during cTBS) (see para 3.3.3)
Transient acute hypomania induction	No	No	Rare	Possible following left prefrontal stimulation	Not reported
Syncope	Possible as epiphenomenon (i.e., not related to direct brain effect)				Possible
Transient headache, local pain, neck pain, toothache, paresthesia	Possible	Likely possible, but not reported/ addressed	Frequent (see para. 3.3)	Frequent (see para. 3.3)	Possible
Transient hearing changes	Possible	Likely possible, but not reported	Possible	Possible	Not reported
Transient cognitive/ neuropsychological changes	Not reported	No reported	Overall negligible (see Section 4.6)	Overall negligible (see Section 4.6)	Transient impairment of working memory
Burns from scalp electrodes	No	No	Not reported	Occasionally reported	Not reported, but likely possible
Induced currents in electrical circuits	Theoretically possible, but described malfunction only if TMS is delivered in close proximity with the electric device (pace-makers, brain stimulators, pumps, intracardiac lines, cochlear implants)				
Structural brain changes	Not reported	Nor reported	Inconsistent	Inconsistent	Not reported
Histotoxicity	No	No	Inconsistent	Inconsistent	Not reported
Other biological transient effects	Not reported	Not reported	Not reported	Transient hormone (TSH), and blood lactate levels changes	Not reported

Adapted from ⁷⁶.

In general, the risks associated with single-pulse TMS are very minimal. Some of the risks that may be associated with TMS include unpleasant temporary side effects including headache, scalp discomfort at the site of stimulation, paresthesia, toothache, hearing changes, spasms, or twitching of facial muscles, and lightheadedness.

Studies suggest that the loud clicking noise produced by the TMS discharge may exceed 140 dB of sounds pressure level, and can cause hearing loss ⁷⁴. However, a majority of studies report no change in hearing after TMS when hearing protection is used ⁷⁴. There is a very small risks of seizures in repetitive TMS done with very intense, high-frequency stimulation or stimulations separated by less than 1 second. Such intensities and frequencies will not be used in this study, as only single-pulse TMS will be employed. A questionnaire⁷⁷ sent to 2510 authors in 174 groups using a variety of coils and protocols in TMS reported over 16 seizures apparently caused by TMS in over 200,000 sessions for a standardized risk of 8/100,000. However, 13 of these occurred in high-risk subjects. The other 3 had no known risk factors ⁷⁴.

Loud auditory stimulus. Loud noises can cause temporary side effects including headache, and discomfort in the ear.

Loss of confidentiality. There is a risk of loss of confidentiality with participation in this study. Investigators will aim to keep the identity of the subjects confidential to the extent permitted by law. However, it is possible that others may become aware of the subject's participation in this study and may inspect and copy records pertaining to this research. Some of these records could contain information that personally identifies subjects.

This is an observational study, and no treatments will be tested in this study. Treatment for SCI will be directed by the participant's physician.

9.4 Procedures to minimize potential risks

This study will be conducted at Washington University under the supervision of the PI. The PI is trained and well-experienced in performing human subject research. Study subjects will be monitored throughout the experiment by a co-investigator. Inclusion and exclusion criteria and monitoring are designed to ensure that the risks are minimal. Subjects are informed that participation is voluntary, and they may refuse to participate and may withdraw from the study at any time without penalty.

The responses to the Beck Depression Inventory questionnaire will be reviewed in real time by team members. If, based on the questionnaires, a participant is suspected of having suicidal intent, the PI will be notified immediately and referrals will be made as needed for further evaluation.

Study staff complete training in HIPPA regulations and do not divulge confidential information regarding participants. Participant records are kept confidential with paper records in a secure location and computer records password-protected, available only to the study staff, and with subject identifiers removed.

Use of motion sensors. To avoid fatigue, experiments will be self-paced by the subject. Subjects will be instructed that they may ask to have the procedure stopped if they have any discomfort or other concerns.

Muscle activity sensors (EMG). Washing the electrode gel from the skin surface and applying unscented skin lotion after the experiments will be applied to minimize skin irritation. Shaving cream will be used to reduce the likelihood of lacerations. In case of lacerations, first aid will be applied as necessary and the EMG application will be discontinued in that area.

Transcutaneous spinal cord and peripheral nerve stimulation. Stimulation will always start at a minimum amplitude and slowly increased as subjects are instructed to give feedback on their comfort levels. Amplitudes will be chosen as the level at which a subject feels paresthesia (tingling sensation) or a motor response is elicited. These amplitudes are normally way below pain thresholds. If a subject feels discomfort at a certain stimulation amplitude, the amplitude will be lowered to a comfortable level, or stopped.

To identify potential incidences of autonomic dysreflexia, blood pressure and heart rate will be monitored before, during, and after the use of continuous SCS. A baseline measurement will be recorded at the beginning of the experiment. A second recording will be performed as soon as the continuous stimulation has reached the amplitude necessary for the experiment. A final recording will be performed at the end of the experiment. Signs of autonomic dysreflexia will include an increase in systolic blood pressure by more than 20 mmHg, absolute pressure greater than 140 mmHg systolic or 100 mmHg diastolic, a decrease in heart rate by more than 40 bpm, face flushing, sweating, and headache. If a sign of autonomic dysreflexia is detected, stimulation

will be immediately stopped, participants will be moved to an upright position to induce an orthostatic hypotension response, and blood pressure and heart rate will be monitored once every 5 minutes until they return to baseline levels.

Transcranial magnetic stimulation. Stimulation will always start at a minimum device amplitude and slowly increase as subjects are instructed to give feedback on their comfort levels. Stimulation amplitudes will be chosen as the level at which muscle responses are elicited. These amplitudes are normally below pain thresholds. If a subject feels discomfort at a certain stimulation amplitude, the amplitude will be lowered to a comfortable level, or stopped.

All participants in our study will be required to wear approved hearing protection (earplugs or earmuffs) during TMS evaluations as recommended by TMS safety guidelines.

Loud auditory stimulus. When delivered continuously for prolonged times (longer than 2 minutes), noises above 110dB can result in temporary or permanent hearing loss. Noises in our experiment will have a short 1/5 second duration to prevent adverse consequences. Subjects will be instructed that they may stop any procedure at any time with no adverse consequences.

Loss of confidentiality. Upon enrollment in this study, 1) all subjects will be assigned a study ID number, 2) The link to identifiers will be destroyed at the end of the study, 3) Data will be stored under lock and key (office, file cabinet) and only the investigators and research team will have access. If data are published, there will be no link to identifiers. Study data will not be revealed to any organization or individuals other than the subjects themselves, 4) Study data will not be entered in subjects' medical records.

Adverse experiences. The investigators will monitor the subjects closely for any local or systemic adverse events from the study. If any such events are noted, they will be managed appropriately and reported to the HRPO and QASMC according to institutional guidelines. Subjects will be followed until satisfactory resolution. The description of the adverse event will include time of onset, duration, severity, etiology, relationship to the study (none, unlikely, probably, highly probable) and treatment that was required.

Premature discontinuation. Subjects may be discontinued from the study if the investigators decide that it is in the best interest of the subject, or the subject requests to be withdrawn. Subjects' participation will be terminated if any significant depression is identified on the collected information on depression. Subjects will also be referred to a mental health professional.

10. Data Safety and Monitoring Plan

The specific monitoring plan for this investigation is commensurate with the risks and the size and complexity of the investigations planned. This study involves a single site (Washington University in St. Louis) and a single intervention (behavioral tasks), with minimal risks. Therefore, we have selected the monitoring authority of: ***[name] and Washington University***

Institutional Review Board.

[name], the Principal Investigator, will take primary responsibility for monitoring participant safety. He will review all serious adverse events (SAEs), adverse events (AEs), and unanticipated problems (UPs) on an ongoing basis, and ensure that the Washington University Institutional Review Board (IRB) receives reports via its online reporting system following the IRB's required timeframes. Specifically:

- All SAEs, regardless of relatedness or expectedness, will be reported to the safety officer within two working days of becoming aware of the event.
- AEs and SAEs that meet the definition of a UP, including breach of confidentiality, will be reported to the safety officer within two working days and to the IRB within 10 working days of becoming aware of the event.
- All other AEs and SAEs that do not meet criteria as a UP will be reported to the IRB at the time of continuing review in accordance with its policy.
- Any major deviations from protocol will be reported within 10 working days, and changes to protocol initiated without IRB approval to alleviate immediate hazards will be reported within 24 hours.
- Participant complaints (which do not rise to the level of UP) and minor deviations from protocol will be reported annually, but any pattern/series of minor deviations will be reported within 10 working days.

In addition, the following records will be added to the study regulatory binder:

- For all reports to the IRB, the Coordinator will retain a copy of the notification to the IRB
- Each SAE and UP will be recorded individually in an Adverse Event Form
- AEs will be recorded as part of the AE Tracking Log.

[name] will ensure that all study personnel are adequately trained and provisioned to work with participants to resolve complaints, trained to identify and respond to expected AEs (e.g. intolerability of spinal cord stimulation or headaches or seizures after transcranial magnetic stimulation), and otherwise trained to ensure compliance with the protocol.

During quarterly whole-study meetings, [name] and the clinical research coordinator will lead a review of any issues related study data and safety with all members of the team.

11. References

1. Center, N. S. C. I. S. Spinal Cord Injury Facts and Figures at a Glance. (2021).
3. Armour, B. S., Courtney-Long, E. A., Fox, M. H., Fredine, H. & Cahill, A. Prevalence and Causes of Paralysis—United States, 2013. *Am J Public Health* **106**, 1855–1857 (2016).

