Transcranial magnetic stimulation (TMS): Motor evoked potentials (MEPs) in the tibialis anterior and rectus femoris muscles will be evoked by TMS of the contralateral motor cortical leg area using a Magstim 200² stimulator (Magstim, UK) through a double cone coil and a monophasic current waveform delivered at 4-s intervals. The motor threshold for both muscles will be identified⁶⁵ and that intensity will be used to elicit and average twenty MEPs at each timepoint²⁴. Average MEP response amplitude will be used to quantify changes in corticospinal tract excitability¹⁵. If no motor threshold is detected at 100% device stimulation intensity due to SCI (and interrupted circuits), the 100% stimulation intensity or the maximum tolerable intensity will be used. MEP responses will be measured during rest and during an active contraction (Motor Tasks, see below) before and after BoMI training, as well as with and without SCS. To estimate changes in MEPs, response amplitudes under different conditions will be normalized to the baseline (before training, resting) response.

Motor tasks: Immediately before after the BoMI session, participants will wear a VR headset (Oculus Quest 2, Facebook, CA) to block their view. The IMUs on the legs will measure and digitize their leg joint angles. A real-time virtual representation of one of their joint angles will be presented through the VR. Participants will be asked to perform two tasks requiring different types of motor control. In the range-of-motion task, participants will be instructed to flex or extend their legs to surpass a virtual target of a specified amplitude. In the precision-control task, participants will have to move their joint and hold the position within a target range of a specified amplitude for 1 second. We will examine motor-evoked potentials elicited by TMS (*Aim 1*) and the StartReact response (*Aim 2*) as individuals perform the task under two conditions: with SCS and without SCS using the knee and ankle joints. As an alternative to the VR headset, a wall projector will be used to perform the motor tasks.

BoMI Training: Participants will perform visuo-spatial motor tasks over a 45min session with SCS. The tasks will consist of different types of game-like activities like center-out reaching, pong, solitaire, Tetris, and other flash games.

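### No blood-pressure reading is required between SCS ramp-up and the end of the experiment, so a symptom-free rise that starts after ramp-up could be found late or missed

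*Combined protocol and SAP*

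**What the plan says.** Section 9.4 of the protocol opens with a general commitment: "blood pressure and heart rate will be monitored before, during, and after the use of continuous SCS". It then names the recordings. The first is a baseline at the start. For the next, "A second recording will be performed as soon as the continuous stimulation has reached the amplitude necessary for the experiment". For the last, "A final recording will be performed at the end of the experiment". Repeat readings appear only once a sign of AD has been found and stimulation stopped: "blood pressure and heart rate will be monitored once every 5 minutes until they return to baseline levels".

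The stop signs include three that are found by measurement: a systolic rise of more than 20 mmHg, an absolute pressure above 140 systolic or 100 diastolic, and a heart-rate fall of more than 40 bpm. Flushing, sweating and headache are also listed.

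The Aim 1 section sets the exposure: "Participants will perform visuo-spatial motor tasks over a 45min session with SCS". It also has motor-evoked potentials (MEPs) measured "before and after BoMI training, as well as with and without SCS". The contingency text in that section allows training to grow to 2 hours if 45 minutes proves too short.

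**The concern.** The pressure and heart-rate stop signs can act only if someone measures while SCS is on. As written, the one reading tied to stimulation comes at ramp-up. That may be minute 0 of training, or earlier if SCS is first switched on for the pre-training tests. The last reading is tied to the end of the experiment, not to SCS being on. The order of the SCS-on and SCS-off blocks after training is not fixed, so SCS may be off by then. One episode described in Section 9.3 resolved within 3 minutes of stopping stimulation, so a normal final reading need not mean that pressure was normal during training.

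A rise already present at ramp-up, or still present at a final reading, would be measured. A rise with symptoms has other routes to detection. What remains is a symptom-free rise that begins after ramp-up. Section 9.3 says blood pressure should be monitored so that AD can be managed in time, and it places the risk in injuries above T6. Such injuries stay eligible under the C4-T9 criterion when there is no history of AD.

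**Working it through.** The plan gives no figure to reproduce, so the check is a count of readings followed by an illustration of delay.

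**Count.** Recordings named in Section 9.4: baseline, working amplitude, end of experiment. Readings required between the second and the third: 0. The interval without a required reading is therefore at least the 45 minutes of training, plus any testing under SCS before it and the testing after it. Under the 2-hour contingency it is at least 120 minutes.

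**Delay for a persistent rise.** The documents give no incidence, onset time or duration for a symptom-free rise, so these are assumptions. Let onset be uniform over minutes 0 to 45 and let the rise persist. In the plan's favour, put the final reading at minute 45 with SCS still on.

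- Current schedule: mean delay 45/2 = 22.5 minutes; maximum 45.
- Readings at 10, 20, 30, 40 and 45 minutes: four 10-minute intervals with mean wait 5, and one 5-minute interval with mean wait 2.5. Mean = (4 × 10 × 5 + 5 × 2.5)/45 = 212.5/45 = 4.7 minutes; maximum 10.
- Readings every 5 minutes: mean 2.5; maximum 5.
- Two-hour contingency, current schedule: mean 120/2 = 60; maximum 120.

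**Sensitivity to onset time.**

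| Onset (minutes) | Current mean delay | 10-minute readings, mean delay |
|---|---|---|
| 0-15 | 45 − 7.5 = 37.5 | (10 × 5 + 5 × 7.5)/15 = 5.8 |
| 15-30 | 45 − 22.5 = 22.5 | (5 × 2.5 + 10 × 5)/15 = 4.2 |
| 30-45 | 45 − 37.5 = 7.5 | (10 × 5 + 5 × 2.5)/15 = 4.2 |

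The 10-minute maximum holds whatever the onset time.

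**A rise that resolves unaided after d minutes.** With one reading at minute 45, the chance of catching it is d/45. For d = 5 this is 5/45 = 11%; for d = 10 it is 10/45 = 22%. With the five readings above, a 5-minute rise is caught if it starts within 5 minutes before any of them: 5 × 5/45 = 56%. A 10-minute rise is always caught.

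**Cost.** Five readings per 45-minute session. At an assumed 1 minute each, 5/45 = 11% of training; at 2 minutes, 10/45 = 22%. Aim 2 follows the Aim 1 protocol, so training is taken to occur at Visits 4 and 5: 12 × 2 × 5 = 120 readings. For the 16 SCI volunteers whom Section 8.4 expects to recruit, the ceiling is 16 × 2 × 5 = 160. Five-minute readings would be 9 per session: 20% of training at 1 minute each, or 40% at 2 minutes.

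**The case against.** The strongest reply is that Section 9.4 already commits to monitoring during SCS, and that the three recordings may be the minimum to document, not a complete list. That reading is possible, and staff may take more readings, but nothing requires one. The final recording can also be defended as the promised reading after SCS. That is fair, but then it cannot also serve as surveillance during SCS.

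The second reply is that other safeguards carry most of the load, and this largely stands. Section 5.2 excludes a history of AD, uncontrolled hypertension, cardiovascular disease, urinary tract infection, pressure sores, unhealed fracture and pain conditions. Amplitude is raised slowly with comfort feedback and normally stays well below pain threshold. A co-investigator watches throughout. Section 9.3 adds "History of AD is already an exclusion criteria of our study, and participants with SCI typically have experience in identifying the onset of AD symptoms". That last safeguard is weaker than it looks, because those with a history of AD, who know the symptoms best, are the ones excluded. All these measures lower the risk, but none measures pressure.

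The third reply is that the harm is hypothetical. This is also correct. Section 9.3 cites a study that looked for AD and found none, and numerous others that reported none. The one participant in fifteen with a systolic rise above 60 mmHg was detected and stimulation was stopped. AD was not confirmed, and the protocol does not say whether symptoms were present.

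A reader might go further and apply the cited rates to this trial: 1 − 0.95^12 = 46%, or 1 − (14/15)^12 = 56%, as the chance of at least one event in 12 participants. The documents do not support that. The 5% comes from children, the 1 in 15 was not confirmed AD, people with a history of AD are excluded here, and neither figure is a rate of late, silent rises.

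**Conclusion.** The gap is real but narrow, and it should be closed. No blood-pressure or heart-rate reading is required from ramp-up to the end of the experiment, including all 45 minutes of training under SCS. The consequence is limited to a symptom-free rise that begins after ramp-up.

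It would be wrong to infer that pressure is never measured under SCS, or that AD is likely to go unnoticed. The ramp-up reading is taken with SCS on, symptomatic AD is covered by observation and symptom signs, and the overall risk is low.

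The most robust figure is the maximum delay for a persistent rise: at least 45 minutes now, against 10 with 10-minute readings, whatever the onset time. The mean delays of 22.5 and 4.7 minutes also need uniform onset. The current-schedule mean further needs a final reading at minute 45 with SCS on, an assumption that favours the present plan. None of this shows that delay causes injury; the documents have no data on that.

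**What to change.** Amend the AD monitoring paragraph of Section 9.4, for SCI participants. Add blood-pressure and heart-rate readings about every 10 minutes during the SCS training session, plus one just before SCS is switched off. Take them between game tasks, and add back any training minutes lost so that the exposure stays at 45 minutes. The investigators and the IRB should confirm the interval. If training is extended to 2 hours, the same interval should carry over.

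The cost is a sentence or two of protocol text and repeats of a measurement already being made: 5 readings per session, about 120 for 12 participants over two visits, or 5 to 10 minutes per session at the assumed 1 to 2 minutes each. Readings at other visits with continuous SCS, such as familiarization, would come on top.

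Two extensions are optional and not part of the cheap fix. Five-minute readings could interrupt 20% to 40% of training. A reading at every switch-on or re-titration could be expensive: if SCS is switched on separately for rest and for each of two tasks at two joints, before and after training, that is (1 + 4) × 2 = 10 per visit, or 10 × 2 × 12 = 240 in all. If any readings are added during MEP testing, they belong between stimulation blocks. Pulses use "a monophasic current waveform delivered at 4-s intervals", so a block of 20 lasts about 20 × 4 = 80 seconds.
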